3.1.4 Pharmacokinetic-Evaluable Population

The pharmacokinetic-evaluable population (PK population) will include all patients who have been randomized to and received any dose of obinutuzumab given as study medication, have at least one post-dose PK sample that is evaluable.

4. STATISTICAL ANALYSES

The primary analysis will be performed when all patients have completed the Week 76 visit or have withdrawn early from the study prior to Week 76, all data collected through

Week 76 are in the database, and the data have been cleaned and verified. At the time of the primary analysis, the study will be ongoing. General Consideration

Analyses of the primary and secondary efficacy endpoints will be stratified by race and region unless otherwise noted. The stratification factors as recorded in IxRS will be used.

All the endpoints will be analyzed and all outputs will presented by combined obinutuzumab and placebo treatment group unless otherwise specified. The treatment group in the document refers to combined obinutuzumab versus placebo group.

Visit windows will be continuous from the midpoint between two consecutive study visits, and will be dependent on the schedule of assessments for each variable independently. The exception will be Week 76 visit window. The upper limit of the Week 76 visit window will be 3 days prior to the next obinutuzumab or placebo infusion or 30 days beyond Week 76 whichever is shorter.

As 24-hour UPCR has been collected less frequently than the spot UPCR, the 24-hour UPCR will be windowed based on spot UPCR's schedule of assessments.

If there are multiple values in the same window, values closest to the scheduled study day will be used in the analysis. If two or more values are equidistant from the scheduled study day, the latest assessment will be used. For each patient, the day of first blinded infusion of obinutuzumab or placebo will be designated study Day 1. Each assessment will be assigned a study day calculated as:

date of assessment -date of first dose +1

Baseline definition: Baseline is defined as the last non-missing value prior to the receipt of blinded infusion of obinutuzumab or placebo. Typically, baseline will be the pre-dose Day 1 assessment, but may include screening results if the pre-dose Day 1 result is not available or missing.

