Treatment failure: Treatment failure is present if any of the following criteria are met:

- New end-stage renal disease (ESRD)
- Need for chronic dialysis
- Need for renal transplantation
- Clinically significant, sustained worsening in UPCR and/or eGFR from Week 24 onward that leads the investigator to conclude the patient has failed the randomized treatment regimen

Receipt of rescue therapy, except for corticosteroid only rescue

Patients with treatment failure must discontinue obinutuzumab or placebo infusions and will be non-responders for all subsequent efficacy analyses. These patients will continue to be followed according to the study schedule of activities through Week 76 and for at least 12 months from the last dose of obinutuzumab or placebo.

Early study withdrawal: Early withdrawal from the study before Week 76 for any reason will be considered as an intercurrent event for the primary endpoint and the secondary endpoints evaluated at Week 76.

As for the secondary endpoints evaluated at visits other than Week 76, the early study withdrawal before the endpoint assessment will be considered as an intercurrent event.

Death: Death before Week 76 for any reason will be considered as an intercurrent event for the primary endpoint and the secondary endpoints evaluated at Week 76.

As for the secondary endpoints evaluated at visits other than Week 76, death before the endpoint assessment will be considered as an intercurrent event.

Study treatment discontinuation: Discontinuation from the blinded obinutuzumab infusion before Week 76 for any reason will be considered as an intercurrent event for the primary endpoint and the secondary endpoints evaluated at Week 76. Any patient who discontinues treatment should continue to undergo protocol-mandated visits.

As for the secondary endpoints evaluated at visits other than Week 76, discontinuation from the blinded obinutuzumab before the endpoint assessment will be considered as an intercurrent event.

4.2.2 Main Analytical Approach for Primary Endpoint

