The proportions of patients achieving CRR in the obinutuzumab (combined treatment groups) and placebo groups will be compared using the CMH test with region and race as stratification factors. The proportion of patients achieving CRR in the obinutuzumab (combined) and placebo groups will be presented along with the adjusted difference, 95% confidence interval (CI) for the adjusted difference, and p-value. A summary of intercurrent events will be produced as well.

Missing data imputation will be performed by multiple imputations using data from patients who did not experience the intercurrent events that are handled using composite strategy, i.e., rescue therapy, treatment failure, death, and early study withdrawal. Prior to applying multiple imputations, missing 24-hour UPCR at any visit will first be imputed by Spot UPCR. Missing UPCR (when both 24-hour and spot UPCR are missing) and eGFR data for the primary endpoint CRR at Week 76 will be imputed by fully conditional specification (FCS) predicted mean matching method. This is also known as multivariate imputation by chained equations (MICE) and will follow the

method described in White et. al (2011). A set of candidate donors with 5 members is chosen for the predictive mean matching method. Separate imputation models will be used for each treatment arm. Only patients who did not experience the intercurrent events that are handled using the composite strategy, i.e., rescue therapy, treatment failure, death, and early study withdrawal, will be included in the imputation model.

UPCR and eGFR will be imputed using a single imputation model. The imputation model will specify UPCR at Week 76 as the dependent variable and will include eGFR at Week 76 as an auxiliary variable to be imputed as part of the MICE procedure. UPCR and eGFR at Week 24, 36, 50, 64 and 76 will be used in the analysis. As 24-hour UPCR is not collected at Weeks 36 and 64, spot UPCR will be used in the models for these time points.

The model will contain the following variables (in order of being imputed):

- Baseline UPCR
- Baseline eGFR
- Log-serum Albumin at Baseline
- Region (stratification factor)
- Race (stratification factor)
- Sex
- Age
- BMI
- Week 24 UPCR
- Week 24 eGFR
- Week 36 UPCR
- Week 36 eGFR
- Week 50 UPCR
- Week 50 eGFR
- Week 64 UPCR
- Week 64 eGFR
- Log-serum Albumin at Week 76
- Week 76 eGFR
- Week 76 UPCR

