- Intercurrent events: Rescue therapy, treatment failure, study treatment discontinuation, or death prior to endpoint assessment. Rescue therapy, treatment failure and study treatment discontinuation will be handled using treatment policy strategy.
 - Death will be handled using composite strategy. Data after death will be imputed by a pre-specified single fixed value specified in the next sections for each of the continuous endpoints.
- Summary measure: Difference in adjusted means at a specified visit of interest

The intercurrent events are described in Section 4.2.1.1.

4.3.1 Key Secondary Endpoints

4.3.1.1 Proportion of Patients who Achieve a Proteinuric Response at Week 76

The proportion of patients who achieve a proteinuric response at Week 76 will be analyzed using a CMH test with region and race as stratification factors. Proteinuric response is defined as achievement of all of the following:

- UPCR < 0.8
- No occurrence of the following intercurrent events:
 - Rescue therapy, treatment failure, death, or early study withdrawal

Missing data: Data obtained from the central laboratory only will be used. UPCR will be imputed by multiple imputations using the model specified in Section 4.2.2. The same imputed datasets produced during the analysis of CRR will be used for the analysis of proteinuric response. The analysis will follow the same methods described in Section 4.2.2.

4.3.1.2 Proportion of Patients who Achieve CRR with Successful Prednisone Taper at Week 76

The proportion of patients who achieve CRR with successful prednisone taper at Week 76 is defined as achievement of CRR (defined as Section 4.2.1) at Week 76 with the following:

 No receipt of prednisone >7.5 mg/day (or equivalent) from Week 64 through Week 76

The endpoint will be analyzed using a CMH test with region and race as stratification factors.

Only oral corticosteroid will be considered for evaluating the no receipt of prednisone >7.5 mg/day (or equivalent) criteria and converted to prednisone equivalent dose when applicable.

Data Handling for Oral Corticosteroids

The study team will monitor oral corticosteroids on an ongoing basis for data quality and to ensure all dose adjustments are being correctly captured. All efforts will be made to resolve missing or ambiguous data prior to database lock. In the case that data queries cannot be resolved, data will be handled in a conservative manner as described in the sections below.

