Early study withdrawals due to reasons other than lack of efficacy will be considered as having missing data.

The missing UPCR and eGFR values will be imputed by the multiple imputation model specified for the primary endpoint in Section 4.2.2 using data from the patients who did not experience death, treatment failure or early study withdrawal due to lack of efficacy.

The death or renal related event endpoint for patients who withdrew early from the study for reasons other than lack of efficacy will then be evaluated based on only the following criteria using the imputed UPCR and eGFR values:

- Worsening proteinuria, defined as a confirmed ≥50% increase in UPCR to a value ≥3
- Worsening eGFR, define as a confirmed ≥30% decrease in eGFR to a value <60

The death or treatment failure will not be imputed.

Worsening proteinuria will be assessed based on 24-hour UPCR which is collected at Week 24, 50 and 76 as per the protocol.

Imputation of eGFR will be made only for the Weeks 24, 36, 50, 64, and 76 as these visits are included in the imputation model (Section 4.2.2). If eGFR values worsened at other missing visits (Weeks 2, 4, 12, 26, and 52) that are not imputed, the worsening due to disease activity should be captured at the next observed or imputed visits. Study withdrawals who have not achieved the event following imputation of their UPCR or eGFR data will be assumed to have not had the event.

The multiple imputation parameters, analysis and pooling steps will be similar to the methods specified in the Section 4.2.2.

4.3.1.5 Mean Change in eGFR from Baseline to Week 76

Change in eGFR from baseline at Week 76 will be analyzed using Analysis of Covariance (ANCOVA) model. The response variable in the model will be change in eGFR from baseline at Week 76. Treatment group (combined obinutuzumab vs. placebo), baseline eGFR and the stratification factors race and region will be included in the model as independent variables. The adjusted difference between the treatment group with 95% CI and p-value will be presented.

The eGFR values for patients who died will be imputed with 0 (composite strategy). All other intercurrent events (specified in Section 4.3) will be handled using treatment policy strategy.

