Missing data will be imputed by multiple imputations using FCS predicted mean matching method. A set of candidate donors with 5 members is chosen for the predictive mean matching method. Only patients who did not experience death will be included in the imputation model. Separate imputation models will be used for each treatment group.

The models will contain the following variables (in order of being imputed):

- Baseline eGFR
- Log-serum Albumin at Baseline
- Region (stratification factor)
- Race (stratification factor)
- Sex
- Age
- BMI
- Week 24 eGFR
- Week 36 eGFR
- Week 50 eGFR
- Week 64 eGFR
- Log-serum Albumin at Week 76
- Week 76 eGFR

The imputation will be implemented using the following three standard steps to generate inference from the imputed data. The number of imputations will be set of 100.

1. Imputation step:

- The missing data will be imputed 100 times to generate 100 imputed datasets for the patients who did not experience death.
- Patients who experienced death will be added in each of the datasets to obtain full datasets including all the patients in the analysis population.
- A number of burn-in iterations of 100 and a seed of 5678234 will be used.
- Analysis step: Each of the 100 imputed datasets will be analyzed using ANCOVA model
- 3. **Pooling step:** The results from the 100 imputed datasets will be combined for inference following the methodology developed by Rubin (Rubin 1987).

4.3.1.6 Change in FACIT-F scale from Baseline to Week 76

Change in FACIT-F scale from baseline at Week 76 will be analyzed using ANCOVA model. The response variable in the model will be change in FACIT-F scale from baseline at Week 76. Treatment group, baseline FACIT-F scale and the stratification factors race and region will be included in the model as independent variables. The adjusted difference between the treatment group with 95% CI and p-value will be presented.

The FACIT-F scale for patients who died will be imputed with 0 (composite strategy). All other intercurrent events (specified in Section 4.3) will be handled using treatment policy strategy.

Missing data will be imputed by multiple imputations. Only patients who did not experience death will be included in the imputation model. Multiple imputation methods will be the same as described in Section 4.3.1.5.

The multiple imputation models will contain the following variables (in order of being imputed):

- Baseline FACIT-F score
- Region (stratification factor)

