- Race (stratification factor)
- Sex
- Age
- Week 24 FACIT-F score
- Week 50 FACIT-F score
- Week 76 FACIT-F score

4.3.2 Supportive Secondary Endpoints

4.3.2.1 Change in Anti-dsDNA Titer from Baseline to Week 50

Change in anti-dsDNA from baseline at Week 50 will be analyzed with ANCOVA model using the same methods described in Section 4.3.1.5. Anti-dsDNA data will be log-transformed before analyzing. The response variable in the model will be change in log-transformed anti-dsDNA from baseline. Treatment group, baseline log-transformed anti-dsDNA and the stratification factors race and region will be included in the model as independent variables. The adjusted difference between the treatment group with 95% CI and p-value will be presented.

The anti-dsDNA values for patients who died will be imputed with upper limit of quantification (ULOQ, 890 IU/mL) of the analytical method used. All other intercurrent events (specified in Section 4.3) will be handled using treatment policy strategy.

Missing data will be imputed by multiple imputations using the same methods described in Section 4.3.1.5.

The models will contain the following variables (in order of being imputed):

- Baseline log-anti-dsDNA
- Region (stratification factor)
- Race (stratification factor)
- Sex
- Age
- Week 4 log-anti-dsDNA
- Week 12 log-anti-dsDNA
- Week 24 log-anti-dsDNA
- Week 50 log-anti-dsDNA
- Week 76 log-anti-dsDNA

Inclusion of Week 76 value in the model has minimal impact on the Week 50 imputation. The Week 76 anti-dsDNA has been added in the imputation model to facilitate the imputation and analysis of anti-dsDNA at Week 76 which is an exploratory endpoint. Also, to facilitate the analysis of anti-dsDNA at other visits, patients who experienced death will be included in the imputation model, but imputed values after death will be replaced by the ULOQ.

4.3.2.2 Change in C3 from Baseline to Week 50

Change in C3 from baseline at Week 50 will be analyzed using the same method described in Section 4.3.2.1. The response variable in the model will be change in C3 from baseline. Treatment group, baseline C3 and the stratification factors race and region will be included in the model as independent variables.

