4.3.2.4 Time to Onset of CRR Over the Course of 76 Weeks

Time to onset of CRR is defined as the time from randomization to the achievement of CRR as defined in Section 4.2.1 for the first time. Based on the schedule of activities, 24-hour UPCR was measured at baseline, Week 24, 50, and 76; Serum creatinine was measured at baseline, Week 2, 4, 12, 24, 26, 36, 50, 52, 64, and 76, through the 76 weeks of treatment visit. The time to onset of CRR over the course of 76 weeks will be either on Week 24, 50, or 76, depending on the timing when CRR is achieved.

Data will be censored as follows:

- Patients who experience the intercurrent events of rescue therapy, treatment failure, death or early study withdrawal before achieving CRR will be censored at Week 76
- Patients completing the 76-week treatment period who do not experience CRR will be censored at Week 76

Time to CRR will be summarized using Kaplan-Meier curves. A stratified log-rank test will be used to compare the treatment groups (combined obinutuzumab vs. placebo) over the 76 weeks treatment period, adjusting for race and region. Median time to event (when estimable), and their 95% CIs, and a p-value from the log-rank test will be presented. The hazard ratio and its 95% CI will be estimated using a Cox regression model stratified by stratification factors. In fitting the Cox model, ties will be handled with the approximate likelihood method of Efron (1977).

Estimand attributes:

- Population: Patients with active or active/chronic ISN/RPS 2003 Class III or IV proliferative LN
- Endpoint (variable): Time to CRR
- Treatments:
 - Experimental: Obinutuzumab 1000 mg IV infusion at Day 1 and Weeks 2, 24,
 26, and either Weeks 50 and 52 or Week 52 only
 - Control: Placebo
- Intercurrent events: Rescue therapy, treatment failure, study treatment discontinuation, death, or early study withdrawal.

Patients who experience rescue therapy, treatment failure, death, or early study withdrawal before achieving CRR will be censored at Week 76

Study treatment discontinuation will be handled using the treatment policy strategy. Patients who discontinued study treatment will be followed for CRR.

Summary measure: Log rank test and hazard ratio

Intercurrent events are described in Section 4.2.1.1 in details.

4.3.2.5 Proportion of Patients who Achieve CRR with Serum Creatinine Criteria at Week 76

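### The imputation model for change in eGFR omits eGFR from Weeks 2, 4 and 12, so a patient who withdraws before the Week 24 window is imputed from baseline variables alone

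*SAP*

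**What the plan says.** - **The model.** SAP 4.3.1.5: "Missing data will be imputed by multiple imputations using FCS predicted mean matching method", with 5 donors, 100 imputations and a separate model per treatment group. It lists baseline eGFR, baseline log-albumin, region, race, sex, age and BMI, then eGFR at Weeks 24, 36, 50, 64 and 76, and log-albumin at Week 76.
- **The primary-endpoint model starts at the same visit.** SAP 4.2.2: "UPCR and eGFR at Week 24, 36, 50, 64 and 76 will be used in the analysis".
- **What is collected.** SAP 4.3.2.4: "Serum creatinine was measured at baseline, Week 2, 4, 12, 24, 26, 36, 50, 52, 64, and 76".
- **The gap is acknowledged for a different endpoint.** SAP 4.3.1.4, on death or renal-related events: "If eGFR values worsened at other missing visits (Weeks 2, 4, 12, 26, and 52) that are not imputed". The SAP expects such worsening to show at the next visit that is observed or imputed.
- **Other models in the SAP use early visits.** The anti-dsDNA model (SAP 4.3.2.1) includes Week 4 and "Week 12 log-anti-dsDNA". The C3 model (4.3.2.2) does the same.
- **Windows.** SAP 4: "Visit windows will be continuous from the midpoint between two consecutive study visits", set separately for each variable.
- **Intercurrent events.** For continuous endpoints, SAP 4.3: "Rescue therapy, treatment failure and study treatment discontinuation will be handled using treatment policy strategy". Deaths receive a fixed value, which is 0 for eGFR. Study withdrawal is not on that list. SAP 4.2.1.1 does say in general that "Early withdrawal from the study before Week 76 for any reason will be considered as an intercurrent event", but neither 4.3 nor 4.3.1.5 gives it a strategy for eGFR change. Values after withdrawal are therefore missing and go to the imputation model.
- **Role of the endpoint.** Change in eGFR is third in the key secondary sequence and is tested at 0.05 or 0.01. Endpoints 4 to 6 are tested only if it is significant (SAP 2.1.1).

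**The concern.** Multiple imputation assumes that, given the variables in the model, the chance of being missing does not depend on the unseen value. If some patients leave because kidney function fell in the first months, that assumption may hold given all the eGFR collected and still fail given only the variables listed. Such a patient would be imputed like a continuing patient with the same baseline, and the recorded fall would have no influence.

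The reassurance in SAP 4.3.1.4 does not help here. It concerns another endpoint, and for someone who has left, the next imputed visit cannot reflect a fall that the model never sees. The planned sensitivity, supplementary and tipping-point analyses (SAP 4.2.3 and 4.2.4) concern the primary endpoint, and 4.3.1.5 names none for eGFR change.

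**Working it through.** **1. The plan's own figure.** The documents state no SD, effect size, power or dropout rate for eGFR. The only figure to reproduce is the primary-endpoint power with 126 per arm and 30% vs 50%: (0.20 − 1.96 × √(2 × 0.40 × 0.60/126)) / √((0.30 × 0.70 + 0.50 × 0.50)/126) = 1.31, so power is 90.5%, against about 90% stated. This confirms the sample size used below and nothing about eGFR.

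**2. Who is affected.** The scheduled days in Protocol Appendix 1 Table 1 are 84 (Week 12), 168 (Week 24) and 182 (Week 26).

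- Week 24 window opens: (84 + 168)/2 = Day 126.
- Week 24 window closes: (168 + 182)/2 = Day 175.

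A sample before Day 126 falls in the Week 2, 4 or 12 window and is unused. A patient with no later sample has only the baseline variables to contribute, because Week 76 albumin is missing too. A patient sampled from about Day 126 on normally contributes Week 24 or later.

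**3. Bias in one arm: method.** Assumptions, not from the documents:

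- SD of change 18 mL/min/1.73 m², baseline SD 28;
- correlation ρ between visits 12 weeks apart of 0.75, 0.85 or 0.95, decaying with time;
- withdrawal after Week 12, more likely the larger the Week 12 fall.

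The slope of Week 76 on Week 12 is ρ^((76 − 12)/12). With overall mean change zero, stayers exceed leavers at Week 12 by fall/(1 − share). So, ignoring baseline,

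bias = share × slope × fall/(1 − share).

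A simulation of 400,000 patients per scenario, using regression imputation in place of predictive mean matching, gave the last two columns.

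| ρ | Share lost | Leavers' Week 12 fall | Slope | Bias by formula | Simulated, listed model | Simulated, Weeks 4 and 12 added |
|---|---|---|---|---|---|---|
| 0.75 | 2.9% | 17.4 | 0.216 | 0.11 | 0.11 | 0.00 |
| 0.75 | 9.8% | 15.0 | 0.216 | 0.35 | 0.34 | −0.01 |
| 0.85 | 2.8% | 17.3 | 0.420 | 0.21 | 0.21 | 0.00 |
| 0.85 | 9.7% | 15.0 | 0.420 | 0.68 | 0.67 | 0.00 |
| 0.95 | 2.9% | 17.3 | 0.761 | 0.39 | 0.38 | 0.00 |
| 0.95 | 9.9% | 15.1 | 0.761 | 1.26 | 1.24 | 0.00 |

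When withdrawal came after Week 24 and depended on Week 24 eGFR, the bias was about 0.00 under both models.

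A cruder product, share × slope × shortfall, shows how far the inputs matter. A 5% loss, a 20 mL/min/1.73 m² shortfall and slopes of 0.4 to 0.8 give 0.4 to 0.8. A 10% loss with a shortfall of 30 gives 1.2 to 2.4.

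**4. Bias in the treatment difference.** This is the gap between the two arms' biases. With about 10% early loss in one arm and 3% in the other: 0.34 − 0.11 = 0.23, 0.67 − 0.21 = 0.46, 1.24 − 0.38 = 0.86. The standard error is 18 × √(2/126) = 2.27, so the bias is 0.10 to 0.38 standard errors. If obinutuzumab had the heavier loss, the one-sided error at nominal 2.5% would be 1 − Φ(1.96 − 0.10) = 3.1% to 1 − Φ(1.96 − 0.38) = 5.7%. If placebo did, the bias would work against obinutuzumab. Equal loss of the same kind gives zero.

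**The case against.** **The route from early decline to missing eGFR is narrow.** Patients who stop infusions complete all visits to Week 76 (Protocol 3.1.4), rescued patients stay on schedule (Protocol 4.4.4.1), and flares may be treated with corticosteroids on study (Protocol Appendix 5). Their eGFR is observed and used. What remains is withdrawal from the study, with no sample from about Day 126 on, for reasons tied to early eGFR. This stands, and it is why the size cannot be fixed.

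**The post-fix result is partly built in.** Withdrawal was generated from Week 12 eGFR, so near-zero bias after adding Week 12 is expected. This also stands. The simulation shows that the fix works if that mechanism operates, not that it does.

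**The anti-dsDNA and C3 comparison is loose.** Weeks 4 and 12 are exploratory endpoints for those markers, which may explain their inclusion. True, so the comparison shows that early visits fit readily into such a model, not that the SAP contradicts itself.

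**An exploratory eGFR slope from Week 12 uses a mixed model that can draw on early values** (SAP 1.1.1.3 and 4.4). It lies outside the alpha-controlled sequence and does not alter the key secondary test.

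**Stronger readings that the documents do not support.** A reader might infer that everyone who leaves early is imputed from baseline alone. In the SAP, early withdrawal means any time before Week 76, and those sampled from about Day 126 on normally contribute Week 24 or later. A reader might also infer that a falling eGFR in someone who leaves is enough to invalidate the imputation. It is not: withdrawal must depend on the omitted value given the listed ones. Nor does leaving out Weeks 26 and 52 produce this problem, since they come two weeks after Weeks 24 and 50.

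**Conclusion.** The point holds for patients who withdraw with their last sample before about Day 126. Their recorded eGFR at Weeks 2, 4 and 12 plays no part in imputing a confirmatory endpoint. If withdrawal depends on that eGFR, the bias is roughly 0.1 to 1.2 mL/min/1.73 m² per arm, under the assumed SD of 18, 12-week correlations of 0.75 to 0.95 and 3% to 10% early loss of this kind. A smaller early fall or weaker persistence shrinks it, and harsher inputs enlarge it.

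The bias in the treatment difference is small against an assumed standard error of 1.9 to 3.1 (SD 15 to 25) and largely cancels if early loss is alike in both arms. It would be wrong to conclude that the plan favours obinutuzumab: the documents give no basis for a direction. This is an inexpensive improvement worth making before unblinding, not a defect that undermines the endpoint.

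**What to change.** Add eGFR at Weeks 4 and 12 to the SAP 4.3.1.5 model. For consistency, add early eGFR and spot UPCR (both scheduled at Weeks 4 and 12) to the SAP 4.2.2 model where it handles withdrawals as missing data: 4.2.4.2.1, 4.2.4.2.2 and 4.3.1.4. The main CRR analysis counts withdrawals as non-responders, so it does not need the change for this reason.

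Weeks 26 and 52 are optional. They add little when Weeks 24 and 50 are observed, though a discontinuation sample may fall in their windows (about Days 175 to 217 and 357 to 406).

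I would not add an indicator for rescue, treatment failure or stopped infusions. Its effect is untested, and because withdrawal itself ends infusions, nearly all leavers could be coded yes, leaving few close donors per arm.

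The cost is SAP wording, a few more variables in existing code and slightly larger imputation models. No new data are needed.
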